**d) Infrared Motion Tracking System (UVA patients only)**

An in-house developed infrared motion tracking system will be optimized at the Emily Couric Cancer Center. The system will initially be validated on 10

healthy volunteers who will be instructed to lie still on the couch for 10 minutes. Following that, a small couch motion of 1-5 mm will be introduced in the x, y and z directions and compared with the motion detected by the infrared cameras. After the system is validated with the healthy volunteers, it will then be used to monitor the intra-fractional motion of patients treated on this protocol during treatment. We anticipate having to modify/edit the software code during clinical implementation.

All patients undergoing treatment at UVA will have “set up” skin marks placed as is standard of care for laser alignment of the patient prior to MVCT scan image guidance, which is then used for finer (generally millimeter) adjustments of internal target volumes. Following scanning we will note the position of the lasers with respect to the set up skin marks, and at the completion of treatment we will again measure the location of the set up marks to the lasers. With this data we can determine if the patient had moved after the image guidance MVCT or during treatment, and we will compare this with data from the infrared tracking system. This system does not utilize ionizing radiation, add additional burdens or constraints, cause any discomfort or side effects, and is completely noninvasive. In reality, an additional layer of safety is added to the STAT RT treatment as any unexpected patient motion will be monitored and reported. We anticipate that this system will be able to accurately track patients with +/- 2-3 mm of motion accurately.

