**e) Optical tracking methods for patient intra-fractional motion monitoring**

At the Emily Couric Cancer Center, we have recently developed an in-house optical tracking system using multiple OptiTrack FLEX:V100 cameras (Natural Point, Corvallis, OR). **See Figure 4**. The camera utilizes 26 infrared light-emitting diodes (LEDs) and a charge coupled device (CCD) to capture the reflective light from markers with special coating. By using multiple cameras, the 3D position of each reflective marker can be determined precisely. Three reflective markers are fixed on a rigid body marker base that can vary in size from a few centimeters to much larger and create a “trackable” that can easily be placed on a patient’s surface to track their motion. **See Figure 5**. The x, y, z, yaw, pitch

and roll of the trackable can be detected by the camera system. An in-house C program was developed to stream the data and display the position of the trackable in real time. Multiple trackables can be placed on a patient and monitored simultaneously. In the lab, localization precision of 0.1 mm was achieved (unpublished data). Through strategic positioning of the trackables, movements of the head, neck, and extracranial locations can be closely monitored. This optical tracking technology is unique to ECCCC and is not available at CRH and patients treated at CRH will not undergo this experimental aspect of the trial.

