Contours generated from the conventional and experimental image registration flows will be compared in a variety of ways as described in Section 7.1. All comparisons of the contouring measures, including the Dice indices, will be performed using paired two-sample t-tests.

Toxicity will be recorded using CTCAE 4.0 criteria and RTOG Late Radiation Morbidity Scoring Criteria. The incidences of grade 3 or more toxicities will be reported.

The effectiveness of the infrared tracking system will be determined by comparing its position calculations with the position of the patient as determined by the position of the lasers with respect to the set up skin marks before and after treatment. The position changes calculated by each method will be compared using paired two-sample t-tests.

The average treatment planning speed of radiation treatment planning with our current clinical system will be calculated and compared the average speed of planning with newer in-development algorithms running on next generation computers with graphic processing units. These means will be compared with two-sample t-tests.

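### In patients the infrared tracker is judged by two laser-to-skin-mark readings, which show only net displacement and so cannot verify tracking of motion within a fraction

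*Combined protocol and SAP*

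**What the plan says.** Objective 2.2.3 has two parts: validate the in-house infrared system, and use it to monitor motion during treatment in patients at the Emily Couric site. Section 7.1 d) describes both.

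- **Volunteers.** Ten healthy volunteers lie still for 10 minutes. The couch is then moved by 1-5 mm in x, y and z, and the imposed shift is compared with what the cameras detect.
- **Patients, purpose.** After that, "it will then be used to monitor the intra-fractional motion of patients treated on this protocol during treatment". Section 1.4, part e), describes a display of position in real time and reports a bench figure: "In the lab, localization precision of 0.1 mm was achieved".
- **Patients, reference.** The first reading is taken after the MVCT: "Following scanning we will note the position of the lasers with respect to the set up skin marks". The second is taken when treatment ends: "at the completion of treatment we will again measure the location of the set up marks to the lasers". The plan then states: "With this data we can determine if the patient had moved after the image guidance MVCT or during treatment".
- **Expected accuracy.** "We anticipate that this system will be able to accurately track patients with +/- 2-3 mm of motion accurately".

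Section 7.3 sets the criterion: "The effectiveness of the infrared tracking system will be determined by comparing its position calculations with the position of the patient", with that position taken from the lasers and skin marks before and after treatment. Section 1.5 says the same. Section 7.3 does not mention the volunteer couch shifts.

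**The concern.** The tracker gives a continuous position record and is meant to detect movement while the beam is on. The reference that decides whether it works in patients is a pair of snapshots. If a patient moves and returns, and the tracker records this correctly, the reference has nothing to match it.

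The reference also has reading error of its own, which the plan does not quantify. If that error is of millimetre size, disagreement at the 2-3 mm scale could come from the lasers, and the effectiveness conclusion would say little about the tracker.

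The protocol hopes to use this component in a later 30-minute workflow and describes it as a further layer of safety. The conclusion drawn here should therefore match what the data can show.

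**Working it through.** **1. What two readings can show.** Let x(t) be the patient's position, with t = 0 just after the MVCT and t = T at the end of treatment. The laser comparison estimates x(T) - x(0).

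- Shift that occurs and stays: x(T) - x(0) is non-zero, so it is visible.
- Shift that occurs and recovers: x(T) - x(0) is near zero, so it is not visible.
- Timing within the interval: not identified in either case.

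**2. How often an excursion would be missed (illustration only).** The documents give no motion model. I assumed 60 time steps per fraction, scaled so that the median peak displacement is 3 mm, and took the fractions whose peak exceeded 3 mm. The share of these with a net end displacement of 2 mm or less was:

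| Assumed motion | Net displacement 2 mm or less |
|---|---|
| Random walk (motion tends to persist) | 22% |
| First-order autoregression, coefficient 0.9 | 77% |
| First-order autoregression, coefficient 0.7 (patient drifts back) | 86% |

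The loss ranges from a minority to a large majority of excursions. It is not total in any of these models.

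**3. Can the reference support +/- 2-3 mm for net displacement?** The plan gives no inputs for that figure, so there is nothing to reproduce. Let s be the SD of one laser-to-mark reading. It is not stated, so a range is assumed, with independent normal errors.

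- SD of the difference = sqrt(2) x s
- 95% band = +/- 1.96 x sqrt(2) x s = +/- 2.77 x s

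| Assumed s (mm) | SD of difference (mm) | 95% band (mm) |
|---|---|---|
| 0.25 | 0.35 | +/- 0.69 |
| 0.5 | 0.71 | +/- 1.39 |
| 1.0 | 1.41 | +/- 2.77 |
| 1.5 | 2.12 | +/- 4.16 |
| 2.0 | 2.83 | +/- 5.54 |

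Solving for s:

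- band within 2 mm: s at most 2 / (1.96 x 1.414) = 0.72 mm
- band within 3 mm: s at most 3 / (1.96 x 1.414) = 1.08 mm

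**4. The same result as a disagreement rate.** For a tracker with no error at all, the two-sided normal tails give the share of fractions in which it would differ from the lasers:

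| Assumed s (mm) | Differs by more than 2 mm | Differs by more than 3 mm |
|---|---|---|
| 0.5 | 0.5% | below 0.01% |
| 1.0 | 16% | 3% |
| 2.0 | 48% | 29% |

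**The case against.** **The accuracy test is already in the plan.** The volunteer step imposes known shifts that span 2-3 mm, comes before any patient use, and matches the separation of validating from monitoring in objective 2.2.3. This stands in part. The step exists, but 7.3 and 1.5 rest effectiveness in patients on the laser comparison, and 7.3 gives the couch shifts no role in the analysis.

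**The net comparison is nearly what is written.** Section 7.3 already refers to position changes computed by each method, and 7.1 d) says unexpected motion will be reported. This also stands, and it is why the fix is small.

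**Stronger readings that a reader might infer:**

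- *The lasers miss all motion during treatment.* They do not, because a shift that lasts to the end is recorded. The sentence in 7.1 d) on whether the patient moved can be read as covering one interval without dating the movement, so it needs qualifying and need not be removed.
- *The reference is known to be coarser than the tracker.* Section 7.1 d) places laser alignment "prior to MVCT scan image guidance, which is then used for finer (generally millimeter) adjustments of internal target volumes". That ranks lasers below MVCT for internal targets and makes no comparison with a surface tracker. The 0.1 mm figure is unpublished laboratory precision, which is not accuracy in patients.
- *The comparison cannot confirm +/- 2-3 mm under any conditions.* That depends on a reading error the documents do not give. An offset common to both readings would cancel in the difference, which helps the reference.

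**Little depends on it.** The +/- 2-3 mm is introduced as an expectation with no pass rule, and the aim is secondary, at one site, and does not affect treatment. All true. This limits the weight of the point but leaves the mismatch between criterion and purpose.

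**Conclusion.** The point holds in a limited form. The comparison that is to determine effectiveness in patients measures net displacement between the post-MVCT and end-of-treatment readings. It cannot verify transient motion or the timing of any motion, and so cannot verify intra-fractional tracking. This follows from the design and needs no assumption.

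Whether the comparison can support the anticipated +/- 2-3 mm, even for net displacement, is conditional. It could not if the SD of one reading exceeds about 0.7 mm (for 2 mm) to 1.1 mm (for 3 mm). It could at 0.5 mm. These thresholds assume independent reading errors, and the documents do not say which case applies.

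The correction is worth making because it changes what the trial can conclude about the tracker at almost no cost. No patient outcome or primary analysis is affected.

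**What to change.** 1. **Section 7.3:** make the 1-5 mm couch shifts in volunteers, already planned in 7.1 d), the accuracy test behind the +/- 2-3 mm statement, comparing imposed with detected shift.
2. **Section 7.3:** in patients, compare infrared end-minus-start displacement with the change in the laser-to-skin-mark reading, and label this a check of net displacement only. Report motion within the fraction descriptively from the tracker record.
3. **Section 7.1 d):** qualify the sentence on whether the patient moved, so that it says the laser readings show net displacement between the post-MVCT and end-of-treatment readings.
4. **Section 1.5:** align the description of how effectiveness is determined.

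The cost is wording in three sections, with no added procedure or patient burden. The downside is a more modest patient-phase conclusion: accuracy would rest on imposed shifts in volunteers, and tracking of movement within a patient's fraction would be described without being verified.

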### **Stopping Rules:**

The study will be suspended for a safety review if 5 or greater “Probable” or “Definite” Serious Adverse Events occur or greater than 5 unexpected toxicities of  $\geq$  Grade 3 occur.

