### **8.1 Definition**

#### **8.1.1 Adverse Event**

An adverse event is any undesirable medical experience occurring to a subject who has been given an investigational product, whether or not related to the study treatment(s). Medical conditions present before starting the investigational treatment/intervention will be considered adverse events only if they worsen after starting study treatment. The following are adverse events:

- All unfavorable, harmful or pathological changes in the general condition of a patient.
- Subjective or objective symptoms (spontaneously offered by the patient and/or observed by the Investigator or the study nurse).
- All intercurrent events or exacerbation of pre-existing diseases which occurred after the administration of the study treatment.
- All clinically significant changes in laboratory abnormalities.

- Any undesirable and unintended effect of research occurring in human subjects as a result of the collection of identifiable private information under the research.

AEs should be followed to resolution or stabilization, and reported as SAEs if they become serious (see below, definition of SAE). This also applies to patients experiencing AEs that cause interruption or discontinuation of investigational product, or those experiencing AEs that are present at the end of their participation in the study. Such patients should receive post-treatment follow-up as appropriate. AEs will be collected up to 30 days post last dose of study treatment in all cases including early study termination. If an ongoing AE changes in its severity or in its perceived relationship to study treatment, a new AE entry for the event should be completed.

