### **8.1.3 Serious Adverse Event**

A serious adverse event or experience (SAE) or serious adverse drug reaction (ADR) is any adverse event temporally associated with the subject's participation in research that meets any of the following criteria:

- Death;
- Is life-threatening (places the subject at immediate risk of death from the event as it occurred);
- Requires inpatient hospitalization or prolongation of existing hospitalization;\*
- Results in congenital anomaly/birth defect;
- Results in a persistent or significant disability/incapacity;
- Important medical events that may not result in death, be life-threatening, or require hospitalization may be considered a serious adverse drug experience when, based upon appropriate medical judgment, they may jeopardize the patient or subject and may require medical or surgical intervention to prevent one of the outcomes listed in the definition. For reporting purposes, also consider the occurrences of pregnancy as an event which must be reported as an important medical event.

\*Hospitalization for anticipated or protocol specified procedures such as administration of chemotherapy, central line insertion, metastasis

interventional therapy, resection of primary tumor, or elective surgery, will not be considered serious adverse events.

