## **8.3 Serious or Unexpected Adverse Event Reporting Requirements**

This section may need revision if Sponsor or Funding Source of study has specific reporting requirements for trial, and/or if study is conducted under an IND.

For any serious or unexpected event which occurs to any patient in the course of their treatment on this study or within 30 days following cessation of treatment, the UVA Study Coordinator must inform:

- **The Principal Investigator verbally within 24 hours.**
- **Written report to the UVA Office of Clinical Research, DSMC, and IRB within 7 days.**

Collection of complete information concerning SAEs is extremely important. Thus, follow-up information which becomes available as the SAE evolves, as well as supporting documentation (e.g., hospital discharge summaries and autopsy reports), should be collected subsequently, if not available at the time of the initial report, and immediately sent using the same procedure as the initial SAE report.

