## **8.4 UVA Cancer Center DSMC AE Reporting Requirements**

All adverse events will be recorded on appropriate case report forms. In addition, AE Reporting will occur via the UVA Cancer Center clinical trials reporting system, C3TO (TABLE Below).

| Therapeutic Medium Risk Phase II Studies   |                         |              |              |          |                         |                      |                         |                      |           |
|---|-------------------------|--------------|--------------|----------|-------------------------|----------------------|-------------------------|----------------------|-----------|
| Reporting requirements for AEs that occur within 30 days of the last dose of protocol specified treatment |                         |              |              |          |                         |                      |                         |                      |           |
|   | Grade 1                 | Grade 2      |              | Grade 3  |                         |                      |                         | Grade 4 & 5          |           |
|   | Expected and unexpected | Expected     | Unexpected   | Expected | Without hospitalization | With hospitalization | Without hospitalization | With hospitalization | Expected  |
| Unrelated   | Not required            | Not required | Not required | C3TO     | C3TO                    | C3TO                 | C3TO                    | C3TO                 | C3TO      |
| Unlikely  |                         |              |              | 30 days  | 15 days                 | 30 days              | 15 days                 | 15 days              | 15 days   |
| Possible  | C3TO                    | C3TO         | C3TO         | C3TO     | C3TO                    | C3TO                 | C3TO                    | C3TO                 | C3TO      |
| Probable  | 30 days                 | 30 days      | 15 days      | 30 days  | 15 days                 | 15 days              | 15 days                 | 15 days              | (24-hrs)* |

|          |  |  |  |  |  |  |  |  |        |
|----------|--|--|--|--|--|--|--|--|--------|
| Definite |  |  |  |  |  |  |  |  | 7 days |
|----------|--|--|--|--|--|--|--|--|--------|

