\*Enter into Cancer Center database within 24 hours if unexpected and definitely related to protocol specified treatment Hospitalization defined as an inpatient hospital stay or prolongation of a hospital stay equal to or greater than 24 hours

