## 8.5 UVA IRB Reporting Requirements

Reporting to the UVA HSR-IRB will follow the institutional plan as outlined in the table below. In addition, DSMC reports will be furnished to the IRB within 15 calendar days of study team's receipt of report.

| Type of Event  | To whom will it be reported: | Time Frame for Reporting   | How reported?   |
|--|------------------------------|--|---|
| Any internal event resulting in death that is deemed DEFINITELY related to (caused by) study participation (Note: An internal event is one that occurs in a subject enrolled in a UVa protocol.) | IRB-HSR                      | Within 24 hours  | IRB Online and phone call
www.irb.virginia.edu/   |
| Internal, Serious, Unexpected adverse event

Only for events as outlined in section 8.0.   | IRB-HSR                      | Within 7 calendar days from the time the study team received knowledge of the event.

Timeline includes submission of signed hardcopy of AE form. | IRB Online
www.irb.virginia.edu/  |
| Unanticipated Problems that are not adverse events or protocol violations  | IRB-HSR                      | Within 7 calendar days from the time the study team received knowledge of the event.   | Unanticipated Problem report form.
http://www.virginia.edu/vprgs/irb/HSR_docs/Forms/Reporting_Requirements-Unanticipated_Problems.doc |
| Protocol Violations (Note the IRB-HSR only requires that MAJOR violation be reported, unless otherwise required by your sponsor, if applicable.)

Or

Enrollment Exceptions          | IRB-HSR                      | Within 7 calendar days from the time the study team received knowledge of the event.   | Protocol Violation and Enrollment Exception Reporting Form

http://www.virginia.edu/vprgs/irb/hsr_forms.html   |

|             |  |  |  |
|-------------|--|--|--|
| Data Breach | The UVa Corporate Compliance and Privacy Office                | As soon as possible and no later than 24 hours from the time the incident is identified. | UVa Corporate Compliance and Privacy Office:
[contact]   |

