### **9.2 UVA Cancer Center Data Safety Monitoring Committee**

The University of Virginia Cancer Center Data and Safety Monitoring Committee (DSMC) will provide oversight of the conduct of this study. The CC DSMC will report to the UVA Protocol Review Committee (PRC).

The DSMC will review the following:

- All adverse events
- Audit results

- Application of study designed stopping/decision rules
- Whether the study accrual pattern warrants continuation/action
- Protocol violations

The CC DSMC will meet every month for aggregate review of AE data. Tracking reports of the meetings are available to the PI for review. Issues of immediate concern by the DSMC are brought to the attention of the PI (and if appropriate to the PRC and IRB) and a formal response from the PI is requested. Per the Cancer Center NIH approved institutional plan this study will be audited approximately every 6 months.

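### The 7.1 suspension rule gives a treatment-related death or permanent disability no separate weight, and the 30-day reporting windows leave late ones uncertainly covered: a cheap improvement, not an error

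*Combined protocol and SAP*

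**What the plan says.** **The rule.** The Stopping Rules under 7.1 are the only study-level suspension provision: "The study will be suspended for a safety review if 5 or greater" SAEs rated Probable or Definite are seen, or if unexpected toxicities of Grade 3 or higher exceed five. No time window, denominator or weighting by seriousness is given.

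**What counts as one event.** Section 8.1.3 lists death, inpatient admission and "Results in a persistent or significant disability/incapacity" side by side as criteria for an SAE.

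**Review and reporting already required.**
- 8.0: any SAE is to be notified to the DSMB and the IRB. No deadline is set.
- 8.3: the PI hears within 24 hours, and the DSMC and IRB receive a written report within 7 days. This covers events "in the course of their treatment on this study or within 30 days following cessation of treatment".
- 8.4: some severe events carry the instruction "Enter into Cancer Center database within 24 hours if unexpected and definitely related to protocol specified treatment". The table is headed "Reporting requirements for AEs that occur within 30 days of the last dose of protocol specified treatment".
- 8.5: a death definitely caused by participation goes to the IRB within 24 hours, with a phone call. The row "Internal, Serious, Unexpected adverse event" allows 7 days. Neither row states a 30-day limit.
- 9.0 and 9.1: the PI monitors safety continuously and reviews all patient data at least monthly.
- 9.2: "The CC DSMC will meet every month for aggregate review of AE data". The DSMC raises matters of immediate concern with the PI and asks for a formal response.

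**Time horizon.** Section 8.1.1 states "AEs will be collected up to 30 days post last dose of study treatment in all cases including early study termination". Yet 5.1 schedules toxicity evaluations to month 12, 1.5 defines late toxicity as starting 3 months after treatment, and the spinal cord row of Appendix F has paralysis at Grade 4.

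**The concern.** The protocol takes care to make severe harm unlikely. Section 1.3.2 rules out the dose distributions behind the severe toxicities it describes, 3.2.9 excludes a PTV within 5 mm of the cord, and Table 2 caps the cord dose at 18 Gy. Against that background, one death or permanent disability judged Probably or Definitely related would be a strong signal. The rule treats it as one-fifth of what is needed to suspend, the same share as a short related admission.

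Two things are at stake. The first is whether further patients start treatment between such an event and the DSMC's review of it. The second is whether a late event, such as a myelopathy found at month 6, reaches the count and the committee in time to protect patients still being enrolled.

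**Working it through.** The plan derives neither threshold, so there is no calculation to reproduce.

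**Inputs.** Thresholds: 5 or more, and more than 5, that is 6 or more (7.1). Planned size: 30 (7.1). Accrual: 18 months (7.1, 7.2) or 24 months (4.1). DSMC interval: one month (9.2). Written report: 7 days (8.3). Visits: 5.1.

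**1. The ceiling.** Let d be the number of Probable or Definite deaths or permanent disabilities, with no other Probable or Definite SAE counted. Let u be the number of these that are also unexpected and Grade 3 or higher, so u is at most d.
- The first limb fires when d is 5 or more. The second fires when u is 6 or more.
- At d = 4 the first limb stands at 4 of 5 and the second at no more than 4 of 6, if no other unexpected Grade 3 or higher toxicity has been counted. Neither fires.
- At d = 5 the first limb fires.

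The largest d without suspension is 4. With one event per patient this is 4/30 = 13.3%. It is a ceiling, because every other related SAE uses up part of the count.

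**2. Patients who could start before DSMC review.**
- Even accrual: 30/24 = 1.25 a month, or 30/18 = 1.67 a month (equal to the 20 a year in 7.2, since 20/12 = 1.67).
- A full month between meetings: 1.25 to 1.67 patients.
- If a 7-day report just misses a meeting, the gap is (30.4 + 7)/30.4 = 37.4/30.4 = 1.23 months, which gives 1.54 to 2.05 patients.

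This is about one or two patients.

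**3. Late events.** Section 5.1 has six post-treatment toxicity evaluations: weeks 1, 4, 8 and 12, and months 6 and 12. Four of the six (week 8 onward) fall after day 30. Late toxicity as defined in 1.5 falls wholly after it.

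Such events can matter while the trial is still enrolling. Under even accrual, patients enrolled at least 3 months before accrual closes number 30 × (18 − 3)/18 = 25, or 30 × (24 − 3)/24 = 26. Those enrolled at least 12 months before number 30 × 6/18 = 10, or 30 × 12/24 = 15. Deaths and withdrawals would lower these figures.

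**4. Pause or report.** Each provision in 8.0, 8.3, 8.4, 8.5 and 9.0 to 9.2 calls for notice, data entry, review or a response from the PI. None stops enrolment. The DSMC's monthly review does not itself require a suspension either, so the ceiling in step 1 applies to the whole study.

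**The case against.** The strongest reply is that a count threshold backed by discretionary oversight is a legitimate choice for a 30-patient pilot. The PI would know of an on-treatment event within a day, the IRB would have a definitely related death within a day, the DSMC would have a written report within a week, and any of them could act. All of that stands. A reader might infer that nobody would look until the fifth event, and the documents contradict that. What they lack is an automatic pause while the review takes place.

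A reader might also infer that four such events could readily fall between two monthly DSMC meetings. Four is the ceiling for the whole study. With 1.25 to 1.67 patients entering a month, four in one interval would need events in several earlier patients to coincide. The realistic exposure is the one or two patients in step 2.

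On late events, a reader might infer that the rule excludes them. It does not say so. Section 7.1 has no window, 8.0 covers any SAE, 8.1.1 requires AEs to be followed and reported if they become serious, 8.5 states no 30-day limit, and the PI's monthly review continues. Late events can be read as counting. What remains is that collection and the DSMC deadlines end at 30 days, so capture and timing are left to interpretation.

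Finally, the number of patients spared exposure by a pause is about the number delayed. That is a fair description of a one-month pause. But stopping enrolment need not withhold palliation, because the department treats such patients outside the trial: 7.1 and 7.2 put the annual number at about 80 and about 30, against 20 accrued.

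**Conclusion.** The point holds as a cheap improvement. The protocol is not in error, and nothing in it suggests that severe events are likely. The rule allows up to four of 30 related deaths or permanent disabilities (13%, a ceiling) over the whole study without a mandatory suspension. About one or two patients could start treatment between such an event and DSMC review. For events after day 30, collection and prompt reporting to the DSMC are not assured by the text.

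The ceiling assumes one event per patient and that no other event has been counted under either limb. The exposure figure assumes even accrual over 18 to 24 months. No probability is given, because the documents state no rate of related death or permanent disability. The vertebral fracture figure in 1.3.2 concerns a different event and should not be used in its place.

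**What to change.** **In 7.1**, add two sentences:
- Any death or permanent disability (for example RTOG Grade 4 spinal cord toxicity) with Probable or Definite attribution, from first treatment through the 12-month follow-up while accrual or treatment is ongoing, suspends enrolment until the DSMC has reviewed it, no later than its next monthly meeting.
- Until then, the PI documents for each patient still mid-course whether the remaining fractions should go ahead.

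Keep the five-event limb for other SAEs. The trigger should say permanent disability, because the disability criterion in 8.1.3 is wider and would suspend enrolment for lesser events. Limiting it to Probable or Definite attribution keeps deaths from the underlying cancer from stopping the study.

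**In 8.1.1, 8.3 and 8.4**, except these events from the 30-day limit, so that they are collected after day 30 and reported on the existing timelines: 24 hours to the PI and 7 days to the DSMC.

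**Cost.** A few sentences that use the existing committee, attribution scale and deadlines. After such an event, enrolment would pause for up to about a month, with one or two enrolments delayed. There would also be a few more late reports.
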